c) **Explain why human subjects must be used for this project. (i.e. purpose of study is to test efficacy of investigational device in individuals with specific condition; purpose of study is to examine specific behavioral traits in humans in classroom or other environment)**

The goal of this study evaluate the efficacy of iTBS-TMS as a treatment for Veterans with an AUD; therefore, humans must be studied.

2. Study Procedures

a) **Please SUMMARIZE the research procedures, screening through closeout, which the research participant will undergo. Sections in the protocol attached in section 16 can be referenced, BUT do not copy the clinical protocol. Be clear on what is to be done for research and what is part of standard of care. For research involving collaborators, please specify the respective roles of Stanford and each collaborator on the protocol.**

PROTOCOL SUMMARY:

Please note: Stanford Co-Investigators who are currently not WOC/Staff at the VA (i.e., Drs. [name], [name], [name]) will not personally execute any study procedure at the VA Palo Alto. Stanford Co-investigators will only be involved in processing and statistical analysis of de-identified neuroimaging, neuropsychological and genetic data.

1. Recruitment and screening: Participants will be recruited via VA Palo Alto Addiction Treatment Services.
2. Informed Consent: Prior to consent, The PI, or Co-I or qualified RA, will recheck inclusion/exclusion criteria.
3. Baseline/Pretreatment Assessment:

Title : Transcranial Magnetic Stimulation for the Treatment of Veterans With Alcohol Use Disorders
Approval Period: 02/28/2025 - 02/28/2026

- Psychiatric Assessment
- Alcohol and Substance use
- Neurocognitive Assessment
- 3 Tesla Magnetic Resonance Neuroimaging: The study will use the 3T UHP system at the Cognitive and Neurobiological Imaging (CNI) facility. The UHP shares a common software and hardware architecture to GE's FDA-approved Premier system but uses a higher-performance gradient coil and is not FDA approved for diagnostic use and is subject to the 21 CFR 812 investigational device(IDE) regulations as well as 21 CFR 50 and 56. The system has been tested by GE according to UL606001-1 and also for compliance with IEC 60601-

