Recruitment and screening: Potential participants from the VAPAHCS treatment programs will be identified based on VA medical/clinical staff diagnoses of an alcohol use disorder without any comorbid condition any conditions that be contraindicated for study (e.g., taking medications that lower seizure threshold, magnetic resonance neuroimaging contraindications, medically confirmed seizure disorder). Specifically, medical/clinical staff of the programs listed above will identify potential participants who meet eligibility criteria and inform the patient that a research opportunity is available to them and offer contact information to study personnel or the participant may request that study personnel contact them. The study has been explained to clinicians via treatment team meetings, so they are familiar with eligibility criteria. The PI, Co-PI or qualified RA will check inclusion/exclusion criteria based on initial eligibility and sociodemographic data via in person screen at the treatment program or at the MIRECC, Building 5, 4th floor. Private interview rooms are available for this purpose at both locations.

Baseline/Pretreatment Assessment see section 2.a.3.b. of grant application:

- a) Psychiatric Assessment: will use standardized measures employed in clinical practice and research.
- b) Alcohol and Substance use: will use standardized measures employed in clinical practice and research. Participants will be asked to submit a urine sample to screen for illegal/non-prescribed drug use and/or complete a breathalyzer to screen for alcohol use.
- c) Neurocognitive Assessment: will use standardized measures employed in clinical practice and research
- d) 3 Tesla Magnetic Resonance Neuroimaging: will be conducted at the VAPAHCS.
- e) Saliva samples: The PI, Co-PI or research assistant will collect saliva samples at Building 5. These samples will initially be stored in a locked cabinet in the PI or Co-Is office at VAPAHCS, Bldg. 5. [name] will then take possession of the participants' saliva samples and take them to the VA-MIRECC Genetics Laboratory for DNA extraction, genotyping and biomarker quantitation

Title : Transcranial Magnetic Stimulation for the Treatment of Veterans With Alcohol Use Disorders
Approval Period: 02/28/2025 - 02/28/2026

at the VA-MIRECC Translational Laboratory. These labs are located in Building 7 at VAPAHCS.

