Design, Treatment Phase and Treatment Arms: This is a double-blind randomized group design, which will enroll 100 participants. After screening and baseline procedures, participants will be randomized to active or sham rTMS conditions (50 active, 50 sham); thus participants will have a 50% probability of receiving active treatment. Participants will receive 20 iTBS-TMS sessions over the course of 2 weeks. Participants will be required to be abstinent from alcohol and illicit substances for 5 days and demonstrate no clinically significant withdrawal symptoms prior to the first iTBS-TMS session.

Rationale for Brain Region Site: The left dorsolateral prefrontal cortex (DLPFC) was chosen as the rTMS stimulation site given excitatory transcranial magnetic stimulation to this region has been demonstrated to decrease cravings in non-Veterans with AUD. Additional stimulation of this site has been robustly shown to be associated with decreased unipolar depressive symptomatology; depressive disorders are highly comorbid in Veterans with AUD.

Duration of Treatment Phase: Active iTBS-TMS Treatment Group – will receive a total of 20 treatments delivered 5-6 days/week. Participants will typically receive two treatments per day (Monday-Friday), over 2 consecutive weeks; inter-treatment interval will be at least 2 hours. However, in the event the participant is unable to complete the typical two iTBS-TMS sessions per day due to participant or research personnel illness, scheduling issues, or other unforeseen circumstances. There have been no adverse events reported in the literature implementing multiple iTBS sessions per day in any population. Sham Treatment group will receive the same frequency and duration of treatment, without actual administration of iTBS-TMS. For both the active and sham iTBS-TMS groups, sessions will typically be conducted prior to the beginning of the participants treatment day, and at lunch, as to not interfere with their treatment-as-usual in the VA substance treatment clinics.

Procedures for Delivery of rTMS Sessions:

1. Anatomical localization of the left DLPFC for the stimulation coil will be individualized for each participant and achieved through standardized procedures for EEG electrode placement, optimized for transcranial magnetic stimulation.

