2. Motor Threshold MT Elicitation: Inherent to the safe and accurate dosing of iTBS-TMS stimulation, resting MT elicitation will be performed according to established protocols, which have been in use since 1994. This protocol is well-established as an effective method for MT Elicitation, widely implemented within both sham-controlled

Title : Transcranial Magnetic Stimulation for the Treatment of Veterans With Alcohol Use Disorders
Approval Period: 02/28/2025 - 02/28/2026

transcranial magnetic stimulation research with demonstrated safety. MT will be calculated for all participants prior to randomization.

3. iTBS-TMS Dosing: Dosing of iTBS-TMS will be delivered at 120% of the participants active MT adjusted to the skull to cortex distance (via each participants structural MRI), as this is documented to modulate the desired cortical target, and is not associated with any adverse events. Six hundred (1200) pulses of iTBS-TMS at 50 Hz will be utilized, consistent with standard parameters. There will be 10 trains of 3 pulses at 50Hz every 200ms (50Hz over 5Hz), which is 30 pulses per theta burst train. Twenty (40) trains will be delivered to achieve 1200 pulses over approximately 6 minutes.

4. Sham Control and Blinding Methods: The sham-control and blinding methods will be the same as used in TMS trials in which investigator and participant blinding to group assignment was carefully documented and achieved in previous clinical trials conducted with Veterans at VA medical centers. These methods involve:

(a) the Cool-B65-Active/Placebo Coil, which functions as both an active and sham coil; (b) scalp electrodes; and (c) a white-noise generator. The scalp electrodes are used to pass a low-voltage, low-electric current (2–20mA at no more than 100V) to mimic the sensation of receiving actual iTBS. The white-noise generator is used to send low-volume white noise to the subject's ears when magnetic stimulation pulses are initiated to hide the click noise the iTBS-TMS produces.

Post-Treatment Phase: Within 3-4 days of completion of the Treatment Phase, all participants will repeat neurocognitive assessment, select psychiatric assessment measures, select alcohol and substance questionnaires, random urine substance screen and alcohol breathalyzer, 3 Tesla Magnetic Resonance Neuroimaging and saliva samples as described above in Baseline/Pretreatment Assessment.

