Transcranial magnetic stimulation (TMS) device: TMS is regarded as safe and without lasting side effects when established guidelines are followed. The primary safety concern associated with any form of transcranial magnetic stimulation procedures are seizures, however, the estimated prevalence is very low at < 1%. In the case of transcranial magnetic stimulation-seizures, all have occurred during stimulation, there was no recurrence of seizures, and no incidences of status epilepticus. All the reported seizures resolved promptly after removal of stimulation, without medical intervention and were not associated with lasting adverse effects. In those rare seizure cases, the motor cortex was typically being stimulated; in the proposed study a non-primary motor region of the cortex (left DLPFC) is the stimulation site. There have been no significant adverse cognitive, brain structural, neurologic or cardiovascular sequelae reported because of TMS. Participants treated with rTMS may experience temporary discomfort at the site of stimulation due to depolarization of sensory and motor neurons in the scalp under the point of stimulation. Muscle tension headache may result in some participants estimated to occur in less than 10% of sessions, and can persist for 1-2 hours post stimulation. rTMS treatment can result in mild to moderate headaches in approximately 15% of participants. These headaches are never disabling or persistent and usually respond to ibuprofen or acetaminophen. The incidence of headaches in those with serial transcranial magnetic stimulation typically diminishes with increasing number of sessions. In some people, particularly those with a history of Bipolar Disorder I or II, daily transcranial magnetic stimulation caused them to experience mania, increased energy, no need for sleep, and racing thoughts; this study will exclude for a history of cyclothymia and Bipolar Disorders.

Magnetic Resonance Neuroimaging: The magnetic resonance scanning devices (3 Tesla, General Electric MR750) used in scanning at the Stanford Center for Cognitive (CNI) and Neurobiological Imaging poses a non-significant risk to subjects in line with the criteria for exception from an IDE, and routinely used by many other investigators at Stanford. There have been no serious adverse events incurred during scanning at the Stanford CNI.

ii. The risks of the Investigational drugs. Information about risks can often be found in the Investigator's brochure.

N/A

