data for each participant, which has been stripped of any information that could be used to identify the participant, may be shared with consultants. However, the participant's personal health information cannot be used for additional research without additional approval from either the participant or a review committee.

Adverse Events (AEs) and Adverse Device Effects (ADEs):

1. Adverse Device Effect (ADE) and Adverse Event (AE)

Definitions:

An Adverse Device Effect (ADE) is defined by 21 CFR 812.3s as any adverse effect/event caused by or associated with the use of a device.

An Adverse Event (AE) is defined by the ICH for Clinical Safety Data as any untoward physical or psychological occurrence in a human subject participating in research. The AE does not necessarily have to have a causal relationship with the pharmacological product, study intervention, or assessment. An AE can, therefore, be any unfavorable or unintended sign (including an abnormal laboratory finding), symptom or disease associated with the use of a medicinal investigational product.

Reporting: In this study, all ADEs and AEs that occur during the acute treatment and follow-up phases will be collected and followed until resolution or the individual's participation in the study ends. All events will be recorded on the appropriate case report form. "Relatedness" involves an assessment of the degree of causality between the study intervention and the event. PIs will be asked to provide an assessment of relatedness. The assessment provided by the PI is part of the information used by the sponsor to determine if the adverse event or effect presents a participant safety concern. An ADE is deemed to be associated with the use of the study device if there is a reasonable possibility that the experience may have been caused by the device or by participation in the trial. Thus, all adverse events or effects with a reasonable causal relationship to the rTMS treatment should be considered related. A definite relationship does not need to be established. The following levels of relatedness will be used in this study:

- Not attributed to iTBS-TMS treatment
- Possibly attributed to the iTBS-TMS treatment
- Attributed to the iTBS-TMS treatment

Serious Adverse Events (SAEs) and Unanticipated Adverse Device Effects (UADEs) Definitions:

Serious Adverse Events (SAEs) are a subset of adverse events and are defined by the ICH for Clinical

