Safety Data Management as any untoward medical occurrence that:

- Results in death
- Is life-threatening
- Requires inpatient hospitalization or prolongation of existing hospitalization
- Results in persistent or significant disability or incapacity
- Is a congenital anomaly/birth defect or
- Any other condition that, based upon medical judgment, may jeopardize the subject and require medical or surgical treatment to prevent one of the above outcomes.

An Unanticipated Adverse Device Effect (UADE) is defined as: Any serious adverse effect on health or safety or any life-threatening problem or death caused by, or associated with, a device, if that effect, problem, or death was not previously identified in nature, severity, or degree of incidence in the investigational plan or application, or any other unanticipated serious problem associated with a device that relates to the rights, safety or welfare of participants. For this study an UADE is considered a category of SAE, which will be reported on the same form.

Title : Transcranial Magnetic Stimulation for the Treatment of Veterans With Alcohol Use Disorders
Approval Period: 02/28/2025 - 02/28/2026

Collection and Recording: For this study, all SAEs and UADEs will be recorded on the SAE form, regardless of cause. The PI will be

asked to determine whether the serious adverse event is related to:

- iTBS-TMS device
- iTBS-TMS treatment
- Medications used to treat AUD and/or co-occurring conditions

Collecting and recording SAEs/UADEs will begin at randomization and will continue throughout the follow-up phase. For a participant who ends study participation prior to the study's completion date, unresolved SAEs will be monitored and reported for 30 days after the End of Study date for that participant. In addition, the investigator must collect all SAEs reported to them for a period of 30 days after the study's completion.

Expedited Reporting of Serious Adverse Events (SAEs) and Unanticipated Adverse Device Effects (UADEs): Study personnel will be responsible for initially evaluating all serious adverse events for participant safety concerns and will confer with the PI as required during this evaluation process. After being reviewed by the PI, any event deemed to be related, serious and unexpected will be reported to study investigators.

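### Adverse-event recording opens at randomization or treatment, after every participant has already had a research MRI and motor-threshold TMS

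*Combined protocol and SAP*

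**What the plan says.** Section 9c sets two recording windows. For serious adverse events (SAEs) and unanticipated adverse device effects (UADEs): "Collecting and recording SAEs/UADEs will begin at randomization and will continue throughout the follow-up phase". For adverse events (AEs) and adverse device effects (ADEs): "all ADEs and AEs that occur during the acute treatment and follow-up phases will be collected". Neither paragraph mentions the baseline period or people who consent but are not randomized.

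Section 2a gives the order of procedures: "After screening and baseline procedures, participants will be randomized to active or sham rTMS conditions". Its baseline list includes a 3 Tesla MRI scan. Under Procedures for Delivery of rTMS Sessions, the motor-threshold (MT) step adds: "MT will be calculated for all participants prior to randomization".

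The seizure rules in 9c stand under a heading that names screening and baseline as well as treatment. They class every seizure as an SAE to be reported to the PI.

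For relatedness of serious events, the PI considers the TMS device, the TMS treatment, and "Medications used to treat AUD and/or co-occurring conditions". The three-level attribution scale for AEs and ADEs refers to iTBS-TMS alone.

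The safety-board paragraph of 9c has study personnel tabulate AEs and SAEs and summarize them for the board.

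**The concern.** Opening the serious-event window at randomization does little harm when nothing investigational happens earlier. Here the study's own TMS device and a research scan are both used first. Section 9c defines an AE as an untoward occurrence in someone taking part in research, which does not depend on randomization, yet its recording windows are narrower than that definition.

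Staff who follow 9c as written have no instruction to complete a study form for, say, a faint during the baseline scan or a headache after threshold testing. The omission is also selective: someone who has a bad experience at baseline and therefore leaves is never randomized and never enters either window. At stake is whether the board sees all events arising from study procedures, and whether a later safety report can account for everyone exposed to them.

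**Working it through.** The main point needs no formula. It follows from setting the order of procedures against the recording rules.

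1. Order, from section 2a: consent, then baseline assessment including MRI, with motor threshold also before randomization; then randomization, treatment sessions, post-treatment assessment and monthly follow-up.
2. SAE/UADE window, from 9c: randomization to the end of follow-up.
3. AE/ADE window, from 9c: acute treatment and follow-up. The start of acute treatment is not defined.

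| Event | Study-form rule in 9c | Result |
|---|---|---|
| Seizure before randomization | Classed as an SAE and reported to the PI, but SAE recording has not begun | Reported; the two rules do not match on recording |
| Other SAE or UADE before randomization | SAE/UADE window not yet open | Outside the recording rule |
| Non-serious AE/ADE at the baseline MRI | AE/ADE window not yet open | Outside the recording rule |
| Non-serious AE/ADE at motor-threshold testing | Depends on whether this counts as acute treatment | Unclear |
| Any of these in a person never randomized | No window named | As in the rows above, with no later window |
| Event caused by the post-treatment MRI | Window open, but no MRI option in the relatedness list | Recorded, but not attributable to the scan on that list |

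The documents give neither a pre-randomization event rate nor the number consented but not randomized, so the expected number of missed events cannot be calculated.

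*Side calculation, relevant only if enrolment is still open.* The seizure rules in 9c suspend enrolment once 10 participants have had a seizure. Section 9a.i puts seizure prevalence below 1% without stating the unit, and no derivation of the 10 is given, so there is nothing to reproduce. If the unit is the participant, take an assumed true rate of 5% (five times the stated ceiling) and let X be the number of participants with a seizure, with X ~ Binomial(n, 0.05):

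P(X ≥ 10) = 1 − Σ(k = 0 to 9) C(n, k) × 0.05^k × 0.95^(n − k)

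- n = 50 (only the active arm carries the risk): expected 50 × 0.05 = 2.5; P = 0.0002.
- n = 100 (everyone carries it): expected 100 × 0.05 = 5; P = 0.03.

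The unit matters. At 1% per session over 20 sessions, the rate per participant is 1 − 0.99^20 = 0.182. About 9.1 of 50 active participants would then be expected to have a seizure, and P(X ≥ 10) = 0.43.

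**The case against.** Starting at randomization is an accepted convention for comparing arms, and events before it cannot be caused by the allocated treatment. That stands for the comparison by arm. It does not justify leaving events from study procedures unrecorded.

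Other routes exist, and they are real. Section 9e.1 has the board review AEs, SAEs and unanticipated problems with no limit by phase. Section 9e.4 requires SAEs to be reported within 24 hours and unanticipated problems within 5 days. The Obligations section requires complications to go to the IRB at once. These routes reduce the chance that a serious event goes unnoticed. They do not tell staff to put pre-randomization events on the study forms.

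Motor-threshold testing can be read as part of treatment: it is a numbered step in session delivery and is not among the baseline items listed in 2a. On that reading, non-serious events from it are covered. The baseline MRI is still not covered, and the explicit start for serious events is unchanged.

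The missing MRI option loses no SAE inside the window, because 9c records SAEs whatever their cause. What it loses is attribution.

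A reader might also infer three stronger things that the documents do not support:

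- That a seizure during threshold testing would go unreported. The seizure rules send it to the PI.
- That the 24-hour rule contradicts the randomization start. It is a deadline counted from learning of an event, not a collection window.
- That a planned final safety analysis would be incomplete. The Data Analyses section specifies no safety analysis; the board's tabulations are the only documented use.

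**Conclusion.** The recording windows in 9c open too late for this design. Before randomization, non-seizure SAEs and UADEs are outside them, as are non-serious AEs and ADEs at least from the baseline MRI. Non-serious events from motor-threshold testing are outside unless that step is treated as acute treatment. For seizures the problem is narrower: the reporting rule and the start of recording do not match.

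The consequence is that such events can be missed in the board's tabulations. It does not follow that they would be missed by everyone, since other routes exist. The gap cannot be given a number from the documents and is best described by the kinds of event listed above. It concerns completeness of safety capture and has no effect on the efficacy analyses. The conclusion rests on reading 9c literally; practice at the site may have been wider than the text.

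The documents do not confirm whether enrolment is closed. The resources section plans recruitment to 06/2023 and section 8m to 30 September 2023, both before the current approval period of 02/28/2025 to 02/28/2026.

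**What to change.** In both 9c paragraphs, start AE/ADE and SAE/UADE recording at informed consent, or at the latest at first exposure to a study device (the baseline MRI or the first motor-threshold pulse). State that people never randomized are included; section 11g already assigns a participant ID after consent, so they can be identified on forms. Tabulate pre-randomization events separately, which leaves the comparison by arm unchanged. Add the study MRI to the relatedness list. The cost is wording in two paragraphs, one added option and a few more forms.

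If enrolment is closed, check source records for pre-randomization events before safety results are reported. That means about 100 participants, plus any consented but not randomized.

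Side note, only if enrolment is still open: state the unit of the seizure prevalence in 9a.i. If it is per participant, ask the safety board to set a trigger below 10, since the present one would rarely fire at a true 5%. This is the board's decision, and the recording fix does not depend on it.
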